## Research Design and Methods

[figure not shown]
### 1. Study Overview

This is a prospective, random assignment, double blind, parallel group pilot study comparing the efficacy of bifrontal ECT performed with ketamine anesthesia to that performed with methohexitol anesthesia in patients with a major depressive episode. We intend over a 2 year period, to recruit 24 patients who are scheduled to receive an acute course of ECT. Patients who are able and willing to provide written informed consent will be randomly assigned on a 1:1 ratio to receive either a course of bifrontal ECT using ketamine or methohexitol anesthesia. Subjects will receive a standard acute course of ECT (3X/week) and depressive symptomatology will be monitored with the Hamilton Rating Scale for Depression (HRSD-24) before each treatment.

The primary outcome will be the number of treatments needed to achieve remission. Remission is defined as two consecutive HRSD scores  $\leq 10$ , and HRSD total score does not change  $> 3$

points or remains < 6 at the last two consecutive treatments. For the secondary aim of this pilot study we will monitor cognitive changes before and after each ECT treatment, and at the end of the treatment course. In addition, we will collect data on other treatment parameters such as seizure duration, electroencephalogram (EEG) morphology, hemodynamic changes, and emergence of any psychotic symptoms post treatment.

Parallel with these procedures we will also collect magnetic resonance imaging (MRI) data on these subjects. The timeline of neuroimaging and its relation to ECT is illustrated in Figure 1.

MRI acquisition will consist of the following: On the day of imaging, the patient will be transported to the North Shore University Hospital 3T GE MRI suite. The patient will undergo an approximately 75 minutes long acquisition session. All subjects will receive structural (e.g., SPGR, FSE, FLAIR, DTI, and spectroscopy) and/or functional MRI exams. During the anatomical, DTI and spectroscopy images, the participating subject will be asked not to move, during resting state fMRI, the subject will be asked to close her/his eyes and not to think anything particular, but to stay awake. During block or event related sessions, the patient will be shown different emotionally loaded images. These images will alternate and the patient will be asked to passively watch these pictures during the five minute acquisition period. These pictures will be chosen from the International Affective Picture System^49, and will be faces expressing different emotions. The International Affective Picture System assigns each image a valence and

an arousal value (derived from testing hundreds of healthy individuals over the span of 13 years). This makes it possible to chose only images with low arousal values (not only to avoid disturbing images but also to filter for nonspecific brain activations), and also to balance out the arousal levels between different emotional domains.

In addition to the imaging procedures detailed above, we also plan to acquire imaging data on healthy individuals with similar timeline. Healthy volunteers will be scanned three times; the first and second scans will be 24-48 hours apart, while the second and third scans will be two weeks apart. The imaging sessions will follow the same protocol as in the patients. The collection of control data is necessary in order to demonstrate that imaging findings are not due to acclimatization to scanner environment or other confounding sources.

## **2. Subject Recruitment**

Twenty four male and female patients with Unipolar or Bipolar Depression who are referred for an acute course of ECT will be recruited for the study. Recruitment will occur at North Shore LIJ-Zucker Hillside Hospital.

The Zucker Hillside Hospital (ZHH) is the major psychiatric facility associated with the health system. Subjects will be recruited from the inpatient and outpatient units. The ECT unit in ZHH is an active unit providing ECT treatments on approximately of 14 patients daily. Prospective subjects will be approached for study enrollment by the ECT psychiatrists who participate in this study and/or a research fellow in ECT. Upon subject's agreement, a meeting with the research staff will be scheduled to begin the informed consent process. The study purpose, procedures, risks, benefits and alternatives will be discussed. After informed consent is signed, eligibility will be confirmed by diagnostic and psychometric assessments by trained raters as described in the screening visit. Based on our previous experience in enrolling patients in other trials, we anticipate that we can accomplish the recruitment goal of 24 patients over two years in the proposed study.

We also plan to recruit 10 healthy subjects for the imaging part of the study, through newspaper advertisement and word of mouth. The wording of the advertisement is attached to this protocol.

## **3. Inclusion/ Exclusion Criteria**

Inclusion Criteria for patients:

1. Male or female subjects 18 to 70 years of age

2. DSM IV diagnosis of Major Depression (296.3), unipolar without psychotic features or Bipolar I or Bipolar II Depression without psychotic features confirmed by SCID-IV interview
3. Pretreatment 24-item Hamilton Rating Scale for Depression score  $\geq 21$
4. Subjects must have an initial score of at least 20 on the MADRS at screen
5. ECT is clinically indicated
6. Patient is competent to provide informed consent

**Exclusion Criteria for patients:**

1. Lifetime DSM-IV diagnosis of schizophrenia, schizoaffective disorder, psychotic depression or any other psychotic disorder as defined in the DSM-IV
2. Current (within the last year) diagnosis of anxiety disorder, obsessive-compulsive disorder, or eating disorder that precedes the onset of the current episode of depression
3. Current diagnosis of delirium, dementia, or amnestic amnesiac disorder
4. Diagnosis of Mental Retardation
5. Baseline Mini Mental State Exam (MMSE) score  $< 21$  or a total score falling two standard deviations below the age- and education-adjusted mean, whichever is less
6. Any active general medical condition or CNS disease which can affect cognition or response to treatment
7. Current (within the past three months) diagnosis of active substance dependence, or active substance abuse within the past week
8. Lifetime history of ketamine or phencyclidine (PCP) abuse or dependence
9. ECT within three months
10. The presence of any known or suspected contraindication to methohexitol or ketamine including but not limited to known allergic reactions to these agents, uncontrolled hypertension, arrhythmia, severe coronary artery disease and porphyria
11. Pregnancy
12. Status 4 or greater according to the criteria of the American Society of Anesthesiologists
13. MRI contraindications

**Inclusion Criteria for healthy volunteers:**

1. Male or female older than age 18
2. Patient is competent to provide informed consent

**Exclusion Criteria for healthy volunteers:**

1. Lifetime history of major chronic mental illness, such as schizophrenia or bipolar disorder
2. Lifetime history of psychiatric hospitalization because of any mental illness
3. Mental illness that needed psychological or pharmacological treatment in the past 3 years
4. Any neurodevelopmental or neurodegenerative disease, or stroke or positive findings on past head CT or brain MRI

5. Pregnancy
6. Lifetime history of ketamine or phencyclidine (PCP) abuse or dependence
7. Current (within the past three months) diagnosis of active substance dependence, or active substance abuse within the past week
8. Hamilton Rating Scale for Depression (HRSD-17) is more than 7
9. MRI contraindications

The majority of these criteria reflect usual clinical characteristics of patients receiving ECT. We include patients with Unipolar and Bipolar depression without psychotic features since recent literature indicate that ECT has equivalent efficacy in Bipolar and Unipolar depressive patients. Moreover, Diazgranados et al in a recent study suggest that a single intravenous infusion of ketamine produced rapid antidepressant effect in bipolar depressive patients. Ketamine was well tolerated and the reported adverse events were similar to those reported in unipolar depressive patients received ketamine. We exclude patients with schizoaffective disorder and schizophrenia because they often require lengthier treatment courses and present with psychotic and cognitive deficits, specific to their illnesses, which may confound our results. We also exclude other diagnostic groups such as patients with neurologic illnesses, dementia, delirium, mental retardation, and active substance abuse/dependence because of possible confounding effects on cognition. Patients who have received ECT within the preceding three months will be excluded for the same reason. Patients who have a lifetime history of ketamine or PCP abuse or dependence will be excluded to protect them from exposure to their drug of abuse or dependence, or in the case of PCP, to a drug similar in mechanism of action. Patients with a current (i.e. within the last year) diagnosis of an anxiety or eating disorder which preceded the current episode of depression will be excluded because their anxiety or eating disorder symptoms may overlap with those of depression and confound psychopathology ratings. Additionally, such patients may have a differential clinical response to ECT. Since we are exploring hemodynamic changes we will exclude pregnant women to avoid confounding the results with the hyper dynamic state of pregnancy.

If during screening the patient is found to be ineligible for the ketamine part of the study (e.g. Hamilton score is low) but patient would undergo ECT for clinical indications, we will still offer the patient to participate in the imaging part of the study, since the patient can still significantly contribute to the secondary aim of this study. In this case (when patient participates only in the imaging part) the inclusion criteria will be only 5, and 6, and the exclusion criteria will be 9, 11 and 13 respectively.

#### **4. Randomization**

**Method:** The permuted block method of randomization will be used to assign patients to one of the treatment conditions. Block size will be varied to minimize the likelihood that the blind will be broken by raters who are blind to assessment. For safety purposes the anesthesiologist and

the ECT psychiatrist will not be masked to the anesthetic agent used. Randomization will be performed by the research coordinator and will be communicated to the ECT psychiatrist and the anesthesiologist.

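### ECT psychiatrists who may recruit also learn each allocation, and varied blocks do not stop better-than-chance guessing, so recruitment should pass to staff not told earlier assignments

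*Combined protocol and SAP*

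**What the plan says.** Three statements in the protocol bear on this point.

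- **Who recruits** (section 2, Subject Recruitment): "Prospective subjects will be approached for study enrollment by the ECT psychiatrists who participate in this study and/or a research fellow in ECT". Research staff then begin the consent process, and trained raters confirm eligibility after consent. Patients are recruited at one hospital.
- **Who learns the allocation** (section 4, Randomization): "Randomization will be performed by the research coordinator and will be communicated to the ECT psychiatrist and the anesthesiologist". For safety reasons, "the ECT psychiatrist will not be masked to the anesthetic agent used".
- **How the sequence is made** (section 4): "The permuted block method of randomization will be used to assign patients to one of the treatment conditions". The only stated reason for varying the blocks is this: "Block size will be varied to minimize the likelihood that the blind will be broken by raters who are blind to assessment".

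The Study Overview plans to "recruit 24 patients who are scheduled to receive an acute course of ECT", assigned 1:1, and no stratification is described. Raters are masked to the agent (section 7a). The documents do not give the block sizes, say whether recruiters share allocations, say whether the fellow learns them, or say what must be recorded before an assignment is released.

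**The concern.** Varying the block size guards against raters working out a patient's arm. Raters do not decide who is approached. An ECT psychiatrist may decide that, and may know earlier allocations because the plan sends them there.

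With 1:1 permuted blocks the arms return to balance at the end of every block. Guessing that the arm with fewer patients comes next therefore works whatever the block sizes are. A recruiter with a view on which agent suits a given patient could decline to approach when the expected arm looks wrong. The protocol supplies grounds for such views: a hypothesis of fewer treatments to remission on ketamine, and a background section on psychotic-like symptoms and raised blood pressure.

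The Data Analysis section says the goal is to estimate effect sizes for a later study, even without statistical significance. A shift in prognosis between arms of 12 would be carried straight into that estimate.

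**Working it through.** **The plan's own figure.** The plan gives no figure for predictability. Its one design figure for the remission comparison is 45% power for 50% against 80% at visit 8, with 12 per arm. The pooled two-proportion formula is Φ{[0.30 − z√(2·0.65·0.35/12)] / √[(0.25 + 0.16)/12]}. It gives 45.6% with z = 1.645 (one-sided) and 32.9% with z = 1.960 (two-sided). That figure is not in dispute here. I take from it only the 12 per arm and the 30-point difference as a yardstick.

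**Step 1: the guessing rule.** Guess the arm with fewer patients so far, and toss a coin when the arms are equal. For one block of 2m, the expected number of correct guesses is m + [2^(2m)/C(2m,m) − 1]/2. For a block of 4 this is 2 + (16/6 − 1)/2 = 2.83, so six blocks give 17.0 of 24 (71%).

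**Step 2: varied blocks, whole sequence known.** Block sizes are an assumption, so a range is shown. The figures come from simulated lists of 24. A guesser who also reasons about where blocks end did no better on correct guesses. The last column counts allocations that can be predicted with certainty by someone who knows which sizes are in use.

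| Block sizes (assumed) | Correct of 24 | % | Known with certainty |
|---|---|---|---|
| Fixed 4 | 17.0 | 71 | 8.0 |
| 2, 4 | 17.3 | 72 | 2.5 |
| 2, 4, 6 | 16.8 | 70 | 0.9 |
| 4, 6 | 16.5 | 69 | 1.4 |
| 4, 6, 8 | 16.1 | 67 | 0.6 |
| No knowledge of past allocations | 12.0 | 50 | 0 |

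**Step 3: partial knowledge.** Suppose patients fall at random to two or three recruiters, and each knows only the allocations of his or her own patients. The same rule then gives about 13.3-13.5 of 24 (56%) with two recruiters and about 13.0 (54%) with three, under all four varied schemes.

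**Step 4: from guessing to bias.** Suppose every informed guess is acted on and shifts the patient's remission probability by +e when ketamine is expected and by −e when methohexital is expected. Correct guesses C exceed 12 by half of (right minus wrong informed guesses). With 12 per arm, the bias in the remission difference is therefore e × 2(C − 12)/12 = e(C − 12)/6.

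- Whole sequence known, e = 10 points: 10 × (16.5 − 12)/6 = 7.5, and 10 × (17.3 − 12)/6 = 8.8. Simulation of blocks {2,4}, {4,6} and {2,4,6} gave 7-9.
- Whole sequence known, e = 20 points: simulation gave 15-17, about half of the planned 30.
- Two recruiters with own patients only (C about 13.4): 10 × 1.4/6 = 2.3 points, or 4.7 at e = 20.
- Three recruiters with own patients only (C about 13.0): 10 × 1.0/6 = 1.7 points, or 3.3 at e = 20.

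With the whole sequence known and no true effect, the two-sided type I error of a simple z-test rose from about 6.5% (its small-sample level) to about 8-9% at e = 10 and about 13-15% at e = 20. This test of proportions stands in for the planned log-rank test.

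**The case against.** The case for leaving the plan alone has real force.

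- **Knowledge is assumed.** A reader might infer that every recruiter sees the whole list and that 67-72% is the expected rate. The documents do not support that. Section 2 speaks of several psychiatrists and/or a fellow, and section 4 sends the assignment to one psychiatrist and the anesthesiologist. Staff in a single unit may share more than their own cases, so 67-72% stands as a ceiling only.
- **Psychiatrists are not the only recruiters.** A fellow may do some or all of the approaching.
- **Varied blocks do help.** A reader might conclude that they give no protection. They cut certain predictions from 8.0 of 24 to 2.5 or fewer. What remains is the informed guess.
- **Steering is constrained.** Patients are already scheduled for ECT, baseline falls within 24 hours before the first treatment, and ECT within three months excludes. An approach therefore cannot be held back freely for a preferred slot. Uncontrolled hypertension, severe coronary disease and psychotic disorders are excluded from both arms, which narrows the motives. Skipping a patient remains possible, and no log of patients not approached is described.
- **Safeguards exist.** The coordinator randomizes, research staff start consent, and masked raters confirm eligibility. These limit selection on measured criteria, but not the choice of whom to approach.
- **The estimate is imprecise anyway.** At 50% against 80% with 12 per arm, the 95% half-width is 1.96 × √(0.41/12), or about 36 points. Imprecision does not excuse an avoidable bias, but it does put one of a few points in proportion.

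**Conclusion.** The point holds as a vulnerability. The plan lets people who receive allocations also choose whom to approach, and its one stated protection is aimed at raters. A recruiter who knows earlier allocations can guess the next one correctly about 54-56% of the time with partial knowledge, and at most 67-72% with full knowledge, against 50% with none. This rests on assumed block sizes and an assumed extent of sharing among recruiters. The bias figures also assume that every informed guess is acted on, which is a worst case.

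A reader might go further and infer that selection will occur, or that the effect estimate is already compromised. Nothing in the documents shows either. The point merits action because the change is cheap and removes the route altogether.

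**What to change.** 1. **Section 2, Subject Recruitment:** have patients approached by the research fellow, or by research staff who are not told earlier allocations, and not by ECT psychiatrists who receive assignments. The coordinator, who performs the randomization, should not recruit either.
2. **Section 4, Randomization:** state that the coordinator releases each assignment only after consent and the masked rater's eligibility confirmation have been recorded.

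The first change brings guessing back to 50% under any block scheme. The second fixes enrolment before the arm is revealed, but would not be enough alone.

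Keep the varied permuted blocks. A single permuted 12:12 list is a tempting replacement, but it is redundant once recruiters do not know past allocations. If they do know them, it still allows 12 + (2^24/C(24,12) − 1)/2 = 14.6 of 24 correct (61%), leaves on average 24/13 = 1.85 final allocations certain, and risks unequal arms if recruitment stops early.

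The cost is wording in two sections and a small reassignment of roles the protocol already names. The fellow must be kept unaware of past allocations, and recruitment may be slightly less convenient. The safety unmasking of the ECT psychiatrist and the anesthesiologist is unchanged.

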### **5. Medication Washout**

As it is common in clinical practice, every effort will be made to discontinue psychotropic medications before the onset of ECT. In any case no psychotropic medications will be allowed 5 days after the first treatment. The only psychotropic medication allowed during the study is lorazepam up to 3 mg/day for anxiety or insomnia.

### **6. ECT Procedures**

ECT will be administered following the standard 3 times per week schedule (Monday, Wednesday, Friday) until remission is achieved (defined by an HRSD-24 score of 10 or less) or until a patient is declared a non remitter (see criteria, page 15). Subjects will be withdrawn from the study if side effects become limiting, or if either the patient or principal investigator determine that ECT should be discontinued. All patients will be treated with moderately suprathreshold stimulus doses. Threshold will be determined at the first treatment and doses will be increased at subsequent treatments as needed to insure adequacy of seizures. (see section d) The average total number of ECT per patient is expected to be approximately 8 and will not exceed 15 in any case.

Both inpatients and outpatients will be brought to the ECT treatment area in the morning on the day of treatment and an intravenous catheter will be introduced and remain in place until the treatment has been completed. Blood pressure, pulse rate, ECG, and pulse oximetry will be monitored prior to anesthetic induction and continuously during the procedure.

#### **a. Electrode placement.**

Standard bifrontal electrode placement will be used in all subjects.

#### **b. Anesthetic procedures.**

Anesthetic procedures will be followed according to the American society of Anesthesia Standard Guidelines. Participants will be instructed to fast for 8 hours prior to ECT session. Approximately two minutes prior to the administration of the anesthetic glycopyrrolate 0.2 mg IV will be administered. Then the anesthetic (either methohexitol 0.5-1 mg/kg or ketamine 1-2 mg/kg) will be administered by rapid bolus injection. After determining loss of consciousness succinylcholine 0.5-1.5 mg/kg IV will be administered. This doses may be adjusted up or down at subsequent treatment sessions depending on the patient's response. Prior to the injection of the succinylcholine a blood pressure cuff will be inflated on the right ankle to 250 mm of mercury to serve as a tourniquet and prevent the flow of succinylcholine to the right foot. This will enable the motor manifestations of the seizure to be observed and recorded. From the onset

of anesthetic response and until the return of spontaneous respiration, patients will be oxygenated with 100% oxygen positive pressure using a Mapelson D circuit. Particular attention will be paid to ensuring hyper-oxygenation prior to seizure induction. Oxygenation will be briefly interrupted during the passage of the electrical stimulus. Pulse oximetry will be used to monitor oxygenation. After ECT administration, participants will be monitored by nursing staff and will not leave the ECT treatment room until they have attained full recovery.

**c. EEG recording.**

A one channel (4-lead) automated EEG recording will be made during each ECT session using left and right fronto-mastoid electrode placements. Pre-lubricated, disposable EEG electrodes will be used (Somatics, Inc., Lake Bluff, IL). The adequacy of the EEG recording will be ascertained prior to the administration of the treatment. In the event of a low-amplitude at baseline, the sensitivity of the EEG amplifier will be increased. The digital recorder strip for the complete treatment session will be retained and identified with the patient's identification number, the date, and the treatment number.

**d. First treatment titration procedure.**

Seizure thresholds are determined at the first treatment. This method, introduced by Sackeim et al allows delivery of a series (usually 1-3) of successively higher stimulations until a seizure is elicited. Two threshold determination schedules are used. One for patients < 50 years of age since younger patients have a lower seizure threshold and the other for patients > 50 years of age or older. Dosing at subsequent treatments is set 50 % above seizure threshold, thereby ensuring seizure adequacy without excessive cognitive effects.

Subconvulsive stimuli (i.e. "missed" seizures) and short seizures during the course are followed by stimuli at 50 % greater charge after a waiting period of at least 20 seconds.

